## Background, Rationale and Context

**1.B. Overview.** Iron is a risk factor for diabetes and one of its principal complications, NASH. Extensive studies in rodent models and small clinical trials in humans have demonstrated significant and even curative benefit from iron reduction by blood donation. This proposal is to perform a larger randomized, placebo-controlled trial that will test the hypothesis that this simple, safe, inexpensive, and even socially beneficial approach is generalizable to a larger population of individuals with prediabetes and early T2DM. In addition to the large trial for efficacy, we propose in subcohorts to investigate mechanism (changes in insulin sensitivity vs. secretory capacity) and to monitor indices of NASH more intensively. In the application, I will first review the data linking iron with diabetes and NASH, present our Preliminary Data supporting efficacy of iron reduction for both conditions, and describe the proposed low-risk clinical trial to test our hypothesis. If iron reduction succeeds in improving glycemic control and affecting NASH progression, the study would have great impact: (1) Although

[figure not shown]

[figure not shown]
Fig. 1: Iron regulation. Iron enters the circulation from the gut via the iron exporter ferroportin (FPN). Transferrin (Tf)-bound iron enters cells after endocytosis of the Tf Receptor. In the liver, iron stimulates production of hepcidin that feeds back to downregulate FPN.

this trial will test the “iron hypothesis” only in those in the upper half of normal iron, and even though that is by definition half of all people with diabetes, the data reviewed below in **1.C** indicate that iron confers excess risk across its entire “normal” range, so most people with diabetes could benefit from iron reduction; (2) The animal models suggest that the beneficial effect of iron will be long-lived, but even if it were to be eventually overcome, for example by continued weight gain, delaying disease onset by only a few years would still have immense benefits in terms of healthcare costs and the delay in the burden of complications those individuals would otherwise suffer; (3) Finally, iron is also associated with other chronic diseases such as Alzheimer’s (see below), and the insights gained in this study may be applied to those conditions as well.

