**Disposition index determined by frequently sampled intravenous glucose tolerance test (FSIGTT) is improved by phlebotomy.** A subset of the subjects (1 control, 8 treated) underwent FSIGTT before and after iron reduction. The disposition index (DI), which is the product of the values for insulin sensitivity ( $S_i$ ) and acute insulin response to glucose (AIRg), serves as a better predictor of diabetes risk than either  $S_i$  or AIRg alone (34). Among the treated subjects, DI improved in seven of eight ( $P < 0.04$  for the entire group, by paired t test). The single control subject undergoing FSIGTT experienced a 72% worsening in DI over the study period. Among all of the subjects, the increase in DI (log transformed) was significantly correlated to the change in ferritin during the study (Fig. 4,  $p < 0.04$ ). The reasons for the improvement in DI varied. Every treated subject improved in terms either of insulin secretion (N=6 of 9, average increase in those 6 of 23.7%,  $p = \text{NS}$ ), insulin sensitivity (N=6 of 9, average increase in those 6 of 51.9%,  $p = \text{NS}$ ), or both (N=3 of 9).

In this small study sample, there was a hint that iron reduction to the very lower limit of normal was not optimally beneficial, and a recent epidemiologic study has suggested a possible optimal ferritin level in the range

of ~40-60 for men and ~30-50 for women, values that are in the 2nd lowest decile of normal.

[figure not shown]

Fig 5. (A) Liver TNF $\alpha$  mRNA, (B) serum ALT, and (C) liver collagen 1 $\alpha$  mRNA in mice fed the

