## METHODS AND MEASURES

**DESIGN:** We propose a randomized, placebo-controlled trial to determine if reducing tissue iron stores by phlebotomy (blood donation) will improve measures of glycemia in Type 2 Diabetes (T2DM) or prediabetes. Adult subjects (N=240 total) aged 40-75, half with prediabetes and half with early T2DM (controlled by diet or up to 2 nonhypoglycemic agents) with ferritin values in the upper half of normal will be randomized to receive real or sham phlebotomy (blood donation), performed in the same manner as at Red Cross donation centers. Glycemia will be assessed by HgbA1C (primary endpoint), fasting glucose, and continuous glucose monitoring (CGM) before and after treatment. Glycemic outcomes will be assessed 6 and 12 months after achieving the target ferritin. The primary endpoint for which this study aim is powered is a change in HgbA1C at 6 months. As secondary outcomes, we will determine if that improvement is stable over a year, and if there are changes associated with iron reduction in serum alanine transaminase (index of NASH), insulin sensitivity by homeostasis model assessment (HOMA-IR), weight, lipids, blood pressure, changes in the number of diabetes medications for participants with diabetes, and changes in glycemic status (normal, prediabetes or diabetes) for participants with prediabetes. We will also correlate the degree of change in glycemia with the starting ferritin levels and the overall change in ferritin to determine targets and thresholds for iron reduction.

There will be two optional sub studies that will be conducted only at Wake Forest Baptist Medical Center. One will look more closely at liver complications of diabetes and the other will explore whether improvements in glucose levels are due to more insulin production or improved insulin action.

Iron may also play a role in the progression of fatty liver to scarring and cirrhosis. Since 75% of people with diabetes have some degree of fatty liver, we would also like to study how your liver reacts to the lowering of iron.

This will require some additional test, namely an MRI and a liver Ultrasound (Fibroscan). There will be approximately 40 people recruited at Wake Forest Baptist Medical Center for the liver sub study.

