### **Glucose Mechanisms Substudy Outcome Measures**

Our primary endpoint will be an improvement in the FSIGTT DI, which is the best predictor of diabetes of the many indices arising from MinMod analysis of FSIGTT data (41). Secondary analyses will be the indices that directly quantify the two hallmarks and principal pathogenic factors in T2DM, namely insulin secretory capacity (AIRg) and insulin sensitivity (Si). As in Aim 2, and as in the pilot study on which this Aim is modeled, we will pool the diabetes and prediabetes groups for the primary analysis. This study is powered for that group analysis based on our preliminary data, although we will subanalyze by subgroups and with ferritin, AIRg, and Si as continuous variables to determine if there is evidence for an optimal ferritin target.

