### **Analytical Plan**

#### **Statistical Plan and Data Analysis.**

The primary analysis will be an analysis of covariance to compare the mean change in the primary endpoint for each aim (HgbA1C at 6 months after phlebotomy for Aim 1, serum ALT at 12 months after phlebotomy for Aim 2, and DI at 6 months after phlebotomy for Aim 3) between the iron depletion and control groups in the full cohort of patients after controlling for the baseline levels of those measurements. The baseline HgbA1C is included as a covariate to increase study power by accounting for regression to the mean between the two time points.

*Secondary Analyses.* The effects of iron depletion on secondary continuous outcomes will be evaluated using analysis of covariance with adjustment for the baseline level of the factor being analyzed as well as the baseline HgbA1C level. For example, we will determine the degree of response (e.g. change in average glucose by CGM) as a function of starting ferritin, ending ferritin, and change in ferritin for determination of dose-response relationships. Treatment effects on dichotomous outcomes (e.g., conversion of pre-diabetes to diabetes) will be evaluated by exact logistic regression, controlling again for the baseline level of the analyzed factor. Ordinal logistic regression will be applied to compare categorical variables with more than 2 ordered categories. In expanded models, interaction terms between the treatment assignment and baseline HgbA1C level will be added to evaluate if the treatment effect differs across the HgbA1C range, and, in particular, between the diabetic and pre-diabetic patients in the study.

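### The mechanism substudy asks about insulin secretion versus insulin sensitivity, but no planned analysis compares the two effects or splits the disposition index effect into its parts

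*Combined protocol and SAP*

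**What the plan says.** The overview (Background, Rationale and Context, 1.B) says that subcohorts will be used to "investigate mechanism (changes in insulin sensitivity vs. secretory capacity"). The DESIGN paragraph puts the same aim as an either/or: "whether improvements in glucose levels are due to more insulin production or improved insulin action". About 48 people will be recruited to this substudy at one site, and the trial randomises 1:1.

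Glucose Mechanisms Substudy Outcome Measures sets the endpoints. The primary is DI: "Our primary endpoint will be an improvement in the FSIGTT DI". On the remaining indices it says: "Secondary analyses will be the indices that directly quantify the two hallmarks and principal pathogenic factors in T2DM". The two it names are AIRg, for secretion, and Si, for sensitivity. The FSIGTT paragraph of the Preliminary Data (1.E) defines DI as an index "which is the product of the values for insulin sensitivity" and acute insulin response.

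Under Statistical Plan and Data Analysis, the primary DI comparison at 6 months controls for baseline DI. Secondary continuous outcomes get "analysis of covariance with adjustment for the baseline level of the factor being analyzed as well as the baseline HgbA1C level". The only further use of AIRg and Si is as continuous variables in the search for an optimal ferritin target.

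**The concern.** The aim is comparative, but the analyses are not. DI combines the two mechanisms. The two secondary ANCOVAs each ask whether one index differs between arms; neither asks whether the effect on one exceeds the effect on the other, or how much of the DI effect each accounts for. A significant result for one index beside a non-significant result for the other is not evidence that their effects differ.

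At stake is whether the substudy, which asks participants to undergo repeated intravenous glucose tolerance tests, can speak to the question it was set up to explore. The pilot shows the difficulty: DI improved (P<0.04), the increases in AIRg and Si were each non-significant, and mechanism was described by counting how many people rose on each index.

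**Working it through.** **1. Does any planned analysis address the contrast?**

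| Planned analysis | What it tests | Separates secretion from sensitivity? |
|---|---|---|
| ANCOVA on DI (primary) | Arm effect on Si × AIRg | No |
| ANCOVA on AIRg (secondary) | Arm effect on AIRg against zero | Not relative to Si |
| ANCOVA on Si (secondary) | Arm effect on Si against zero | Not relative to AIRg |
| Ferritin, AIRg and Si as continuous variables | Optimal ferritin target | No |

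**2. The plan's own figure.** Statistical Power gives N = 16 for DI, from a within-subject comparison at 80% power. No mean or SD for DI is given, so 16 cannot be reproduced. It implies a standardised change of (1.960 + 0.842)/√16 = 0.70, or 0.75 with the t distribution. Nothing is stated for AIRg or Si.

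**3. What two p-values read side by side would show.**

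Inputs from the documents: 48 people at 1:1 gives 24 per arm. The 20% dropout allowance under Sample Size gives 24 × 0.8 ≈ 19. Alpha is 0.05, taken as two-sided.

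Assumptions not in the documents: equal true effects d on log AIRg and log Si, equal residual SDs, and a correlation ρ between the two residuals from -0.5 to +0.5.

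Worked case with 24 per arm, d = 0.6, ρ = 0: noncentrality is 0.6 × √(24/2) = 2.08, so each test has power 0.53. Then:
- exactly one significant: 2 × 0.53 × 0.47 = 0.50
- both: 0.53² = 0.28
- neither: 0.47² = 0.22

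Simulated percentages (40,000 trials per cell, two-sample t tests) as exactly one / both / neither, rounded:

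| Per arm | d | ρ = -0.5 | ρ = 0 | ρ = +0.5 |
|---|---|---|---|---|
| 24 | 0.4 | 49 / 3 / 48 | 40 / 8 / 53 | 28 / 14 / 59 |
| 24 | 0.6 | 65 / 21 / 15 | 50 / 28 / 22 | 34 / 36 / 30 |
| 24 | 0.8 | 42 / 57 / 1 | 34 / 61 / 5 | 25 / 65 / 11 |
| 19 | 0.4 | 42 / 2 / 57 | 35 / 5 / 60 | 25 / 10 / 65 |
| 19 | 0.6 | 63 / 12 / 25 | 49 / 19 / 32 | 34 / 27 / 39 |
| 19 | 0.8 | 56 / 39 / 5 | 44 / 45 / 11 | 30 / 52 / 18 |

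Exactly one test is significant in 25% to 65% of trials. That is the largest of the three outcomes in only 6 of the 18 cells, once by a single point.

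**4. Scaled to the plan's N = 16.** Take 0.70 to 0.75 as the between-arm effect on log DI, in SDs. With equal contributions, each component effect is d = d_DI × √(2(1 + ρ))/2; for example, 0.70 × √2/2 = 0.49 at ρ = 0. Over ρ from -0.5 to +0.5, exactly one test is significant in 33% to 51% of trials at 24 per arm and 34% to 47% at 20 per arm. Neither is significant in 24% to 58% at 24 per arm.

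**5. The direct comparison.** The difference log AIRg minus log Si has residual SD √(2(1 - ρ)) in component SD units. When the contributions are equal, its test rejects about 5% of the time (4.9% to 5.2% in simulation). If only one mechanism acts, at 0.6 SD and 24 per arm, the noncentrality is 0.6/√(2(1 - ρ)) × √12. Power is 22% at ρ = -0.5, 30% at ρ = 0 and 53% at ρ = +0.5. The 95% CI half-width is 2.01 × √(2/24) × √(2(1 - ρ)), which is 1.01, 0.82 and 0.58 SD respectively.

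**6. Additivity.** Because log DI = log Si + log AIRg, and ANCOVA estimates are linear in the outcome, the AIRg and Si arm effects sum exactly to the DI effect when all three models share the same covariates. With each index adjusted for its own baseline they need not. In simulation the gap had an SD of about 0.03 around zero, with no bias.

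**The case against.** The strongest reply is that nothing in the plan says mechanism will be decided by which p-value falls below 0.05. A reader might infer that the substudy will often credit a single mechanism when both contribute equally. The documents do not support that: no attribution rule is written, and the pilot report kept a category for people who improved on both indices and said the reasons for improvement varied. This stands. The percentages above describe a possible misreading, not a planned error.

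The aim is also worded as exploratory, in lay language, while the formal endpoint section puts DI first and is powered for DI. Separate arm effects on AIRg and Si do describe what changed. That lowers the importance of the point. It does not remove it, since both statements of the aim are comparative and an exploratory question still needs an analysis directed at it.

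A reader might also infer that a split result is the likeliest outcome. Across the assumed range it is not: neither test tends to be significant at 0.4 SD, and at 0.8 SD with 24 per arm both usually are. Positive correlation lowers the split rate to 25% to 34%. Nor is the covariate mismatch a material source of error: the gap is small and unbiased, and the plan does not specify a log scale for AIRg and Si in the first place.

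Finally, the direct comparison has low power. This stands too, and it argues against a rule that credits a mechanism only when the CI for the difference excludes zero.

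**Conclusion.** The gap is real: the secretion-versus-sensitivity question appears in two places, and no planned analysis addresses it. That conclusion rests on the text alone.

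The size is conditional. If the two tests were read side by side, exactly one would be significant in about 25% to 65% of trials with equal true contributions. This assumes effects of 0.4 to 0.8 residual SD, equal SDs, 19 to 24 per arm, and correlation from +0.5 to -0.5. A direct test of the difference would be wrong about 5% of the time in the same situation.

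This is a secondary question in an optional, exploratory substudy. It does not touch the HgbA1C primary analysis or the DI endpoint itself. It is worth correcting because the correction is cheap.

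**What to change.** In Glucose Mechanisms Substudy Outcome Measures and the Statistical Plan:

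- Analyse log AIRg, log Si and log DI with one common covariate set: arm, baseline log AIRg, baseline log Si and baseline HgbA1C.
- Report the AIRg and Si arm effects with 95% CIs as the two additive parts of the DI effect.
- Report the difference between the two effects with its 95% CI.
- State that significance of one index and not the other will not by itself be taken as evidence that one mechanism predominates.

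The cost is a few lines of text, with no new data, visits or participants. Logs need positive values, so the plan should say beforehand how any zero or negative value is handled. If the sponsor prefers to keep baseline DI alone in the primary DI model, the decomposition can be a supporting analysis.

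The drawback is imprecision: with about 24 per arm and one mechanism acting at 0.6 SD, the difference would be detected only about 22% to 53% of the time. The result may be that the mechanisms cannot be separated, and the plan should say so in advance.

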### **Subjects selection criteria**

Subjects will have type 2 diabetes mellitus, or prediabetes, defined by HgbA1C criteria.

- **Inclusion Criteria.** Ages 40-75; At least 3 months since diagnosis of prediabetes or diabetes; HgbA1C value within three months or at screening of 5.7-6.4% for those with prediabetes, undiagnosed on no medication HgbA1C 6.5-6.9 and 7-8.5% for those with diabetes (the upper limit of the latter to reduce the likelihood of major changes in glycemic intervention during the trial period, and the lower limit to allow some room for improvement); Serum ferritin levels within 1 year or at the time of screening in the upper half of the normal range (>50 ng/mL for women and >100 ng/mL for men). C-reactive protein levels up to 11.0. Subjects will be on stable lifestyle therapy and 0-2 antihyperglycemic agents that are non-hypoglycemic (i.e. no sulfonylureas, glinides or insulin) to limit the chances of hypoglycemia if, as hypothesized, participants become more insulin sensitive with iron reduction. Aim 2 – serum ALT> 1.5 times the upper limit of normal, or; liver stiffness of > 12.5 kPa by Fibroscan transient elastography.
- **Exclusion Criteria.** Documented current anemia, hemoglobin levels within 0.5 g/dL of the lower limit of normal (<12.5 g/dL for women and 13.5 g/dL for men), or recent blood loss; bleeding diatheses (coagulation abnormalities or treatment with anticoagulants); serious chronic infections or chronic inflammatory conditions that could elevate ferritin as an "acute phase reactant;" C-reactive protein greater than 10.0, the upper limit of normal, to further validate the lack of significant chronic inflammation; active cancer diagnosis (excluding skin cell cancers other than melanoma); renal insufficiency (eGFR<60 ml/min); history of orthostatic hypotension; heavy alcohol use (NIH criteria, for men greater than 4 drinks on any day or 14/week, for women >3 drinks on any day or > 7/ week); pregnancy or premenopausal women of childbearing age, unless unable to become pregnant because of oral contraceptive use, IUD, birth control implants, surgical loss of ovaries or uterus. Aim 2 – individuals meeting the additional inclusion criteria for aim 2 will be tested for anti-HAV IgM, HBs Ag, anti-HBc. IgM, anti HCV IgM and IgG. Subjects who prove positive for any of these viral serologies, except for HCV IgG will be excluded. The latter will be tested for HCV RNA by PRC, and if negative they will be eligible for enrollment
- **Sample Size.** In our pilot study of the effects of phlebotomy, we did not measure HgbA1C, but did perform glucose tolerance testing where the difference in area under the curve from pre- to post-treatment was  $1130 \pm 1970$  mg-min/dl. Assuming this average change would be maintained through the day, and converting this change to the relative change in HgbA1C, the change would be expected to be a decrease of ~0.6% (in A1C units, not a change of 0.6% magnitude). With the variance observed, this means a sample size of 32 patients in each group will provide 80% power to detect a difference between the beginning and final HgbA1C in either treatment group at  $p < 0.05$  when pre- and post-phlebotomy results are compared within subjects. This agrees with the published results from another group that did measure HgbA1C, wherein they achieved a significant change ( $p < 0.001$ ) with an N of 31, but a shorter observation period and much less reduction in ferritin. A larger sample size (60/group, 240 total in Aim 1, half diabetes and half prediabetes, with

120 each being randomized to control and phlebotomy) will be recruited to facilitate possible subgroup analysis (e.g. stratification by age, treatment, race, sex) and to allow an up to 20% dropout rate, which is significantly higher than the experience of previous similar studies at Wake Forest University, wherein the dropout rates were in the 12-15% range. (In our pilot study, there were no dropouts.) Thus, we will be theoretically powered to analyze each target ferritin group separately, although the initial analysis will pool the two treatment groups.

- **Multisite study.** This is a multisite study, coordinated by WFUHS, and equal numbers will be recruited at each site, 120 at WFUHS and 120 at UNC Chapel Hill. The Liver substudy will recruit 40 people and the Glucose Tolerance Mechanism substudy will recruit 48 people. The sub studies will be conducted only at Wake Forest Baptist Medical Center.

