**1.E. Preliminary Data: Phlebotomy for prediabetes and T2DM).** To demonstrate the benefits of reducing iron on glucose homeostasis, we recently completed a pilot study in which subjects (N=11, 9M and 2F, aged  $57.2 \pm 1.2$  yr, BMI  $30.6 \pm 2$  kg/m^2) with prediabetes (N=3) or early T2DM (N=8) were treated with phlebotomy in order to reduce serum ferritin concentrations. No subjects had evidence of systemic inflammation as assessed by medical history or elevated C-reactive protein. Individuals treated with phlebotomy achieved a significantly lower serum ferritin level with biweekly to monthly 1 Unit donations (average  $3.4 \pm 0.5$  Units, or  $\sim 1.7$  L) of blood, providing further evidence that the elevations in ferritin were related to iron and not inflammation. Women started with lower ferritin ( $92 \pm 2$  ng/mL) compared to men ( $219 \pm 32$  ng/mL,  $p < 0.04$ ) and thus achieved less absolute lowering of their ferritin ( $56 \pm 7$  ng/mL) than did the men ( $150 \pm 33$  ng/mL). Average weights increased slightly but not significantly in both groups over the course of the study (1.8 kg in treated, 3.1 kg in controls,  $p = \text{NS}$ ). Blood hemoglobin concentrations tended to decrease in the treated group ( $p = 0.10$ ); only one subject declined to below the normal range (by 0.1 g/dL, less than 1% below normal) and recovered to normal by the end of the study. There were no serious adverse events and no fainting.

**Improved glucose tolerance after phlebotomy.** Phlebotomy treatment resulted in significant lowering of

area under the glucose curve (AUCg) during a 120 min oral glucose tolerance test (average improvement  $1340 \pm 570$  [mg/dL]\*min,  $p < 0.05$  by paired t test). Non-treated controls increased their AUCg value by an average of  $1110 \pm 670$  (mg/dL)\*min, significantly different from the treated group (Fig. 3,  $p < 0.04$ ). The decrement in the AUCg after phlebotomy tended to be correlated with the starting AUCg value ( $r = 0.667$ ,  $p = 0.13$ ) and the starting ferritin value ( $r = 0.641$ ,  $p = 0.063$ ). AUCg values also trended to decrease more in those with prediabetes than diabetes ( $-10.3 \pm 2.2\%$  compared to  $-2.9 \pm 2.3\%$ ,  $p = 0.06$ ), suggesting that early intervention, perhaps before critical loss of beta cell mass, will prove to have the greater beneficial effect.

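### The pilot mean AUC change behind the sample size (1130) is not the mean reported for that pilot (1340), and 32 per group at 80% power follows from neither figure

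*Combined protocol and SAP*

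**What the plan says.** Section 1.E (Preliminary Data) introduces the pilot with the words "we recently completed a pilot study in which subjects (N=11, 9M and 2F, aged"; the age given is 57.2 ± 1.2 years, and these subjects all received phlebotomy. Its glucose-tolerance result concerns "area under the glucose curve (AUCg) during a 120 min oral glucose tolerance test (average improvement". The figure reported there is 1340 ± 570 [mg/dL]*min, with p<0.05 from a paired t test. On the comparison group it adds "Non-treated controls increased their AUCg value by an average of"; the figure is 1110 ± 670.

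The Sample Size bullet under Subjects selection criteria notes that the pilot has no HgbA1C data. It states instead that the investigators "did perform glucose tolerance testing where the difference in area under the curve from pre- to post-treatment was"; the value given is 1130 ± 1970 mg-min/dl. The step to HgbA1C is described as "Assuming this average change would be maintained through the day, and converting this change to the relative change in HgbA1C", and it leads to an expected fall of about 0.6 A1C units. The size is then stated: "With the variance observed, this means a sample size of 32 patients in each group will provide 80% power". The test in question sets HgbA1C at the start against HgbA1C at the end for either arm, at p<0.05, and the bullet specifies that this applies "when pre- and post-phlebotomy results are compared within subjects".

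The Statistical Power paragraph of the Analytical Plan repeats 1130 ± 1970, the 0.6 and the 32. No section labels either ± as SD or SE, gives the number of subjects in the AUC test, or mentions a second set of pilot subjects or a second calculation.

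**The concern.** Both figures are presented as the pilot's pre-to-post change in glucose AUC, in equivalent units and in the same direction. Rounding cannot turn 1340 into 1130. The pilot is the only source for which the plan states both an effect and a spread, and the effect assumed for the primary endpoint is converted directly from this mean. A reader who tries to follow the sample size back to its source finds a different number there. The recruited total is not what is at stake. The question is whether the stated size and power can be reproduced from the pilot, and whether the figure used for planning agrees with the significance claimed for the pilot in the rationale.

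**Working it through.** **Inputs.** Planning figure: mean 1130, spread 1970 (Sample Size; Statistical Power). Reported figure: mean 1340, spread 570, p<0.05 (Section 1.E). Stated design: 32 per group, 80% power, p<0.05, within-subject comparison. Two assumptions are needed. Alpha is taken as two-sided, since the plan does not say. The n in the AUC test is taken as 11, with other values shown, since it is not given.

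**1. The stated 32.** Read 1970 as the SD of the change. Standardised effect d = 1130/1970 = 0.574.
- Normal approximation, 80% power: n = ((1.960 + 0.842)/d)² = 23.9, so 24.
- Exact paired t, 80% power: 25.8, so 26.
- Power at n = 32, exact paired t: 88%.
- Effect for which 32 gives 80% power: d = 0.511.

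So 32 is not reproduced at the stated power. It does appear at 90% power with the normal approximation: ((1.960 + 1.282)/d)² = 31.9. Inflating 26 for 20% dropout gives 26/0.8 = 32.5, which rounds up to 33. Neither is the calculation described: the stated power is 80%, and the dropout allowance is applied to the 60 per group.

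**2. The means.** 1130/1340 = 0.843, a difference of 16%.

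**3. The spreads.** If 570 is an SE, t = 1340/570 = 2.35, and p = 0.041 at n=11 or 0.047 at n=9. Both agree with the reported p<0.05. If 570 were an SD, p at n=11 would be about 0.00001, far below the reported threshold. So 570 behaves as an SE, and the implied SD is 570·√n:

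| n | implied SD |
|---|---|
| 9 | 1710 |
| 11 | 1890 |
| 12 | 1975 |

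Against 1970, the gap is 13% at n=9, 4% at n=11 and under 1% at n=12. The spreads are broadly compatible once one is an SE and the other an SD.

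**4. The planning pair against the reported significance.** With 1970 as SD, t = 1130/(1970/√n):

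| n | t | two-sided p | one-sided p |
|---|---|---|---|
| 9 | 1.72 | 0.124 | 0.062 |
| 11 | 1.90 | 0.086 | 0.043 |
| 12 | 1.99 | 0.072 | 0.036 |

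Two-sided p stays above 0.05 for every n from 6 to 14. If 1970 were an SE, t = 1130/1970 = 0.57 and p = 0.58 at n=11.

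**5. Sample size from the Section 1.E figure.** Exact paired t, 80% power, two-sided 0.05:
- n=11: d = 1340/1890 = 0.709, needing 17.6, so 18. Power at 32 is 97%.
- n=9: d = 1340/1710 = 0.784, needing 14.8, so 15. Power at 32 is 99%.

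The stated 32 exceeds what either figure requires.

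**The case against.** The strongest reply is that the two figures need not describe the same subjects. Section 1.E hints that n varied between its AUC analyses. A correlation of 0.641 with p=0.063 fits n=9, whereas 0.667 with p=0.13 falls between n=6 and n=7. The FSIGTT analysis used a further subset (eight treated, one control). Two means from different subsets could both be right. The p<0.05 is also attached to 1340 ± 570, with which it agrees, and was never claimed for 1130 ± 1970. A one-sided test would bring the latter to p=0.043 at n=11. Finally, the planning figure is the less favourable one, the plan also cites a published study (N of 31, p<0.001), and the 240 was set for subgroups and dropout.

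Most of this stands, and it rules out two stronger readings. A reader might infer that the variance also contradicts its source. The SE/SD reading above shows that it need not. A reader might also infer that one of the two figures must be wrong. That requires the same subjects and the same n, which the documents do not establish.

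The reply does not remove the gap. The plan presents the planning mean as the pilot's result without naming a subset, so the different-subjects explanation is a conjecture that only the sponsor can confirm. The published study is cited without an effect or variance, so it cannot verify the input. Nor does any of this make 32 follow from the stated 80% power.

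**Conclusion.** The point holds for the mean and for the stated size and power. The mean used for planning is 16% below the mean reported for the same pilot, without explanation. Paired with an SD of 1970 it does not give the reported two-sided significance at any n from 6 to 14. The 32 per group at 80% power follows from neither figure: 1130/1970 needs 26 and gives about 88% power at 32, and Section 1.E needs 15 to 18. Using the lower mean errs on the safe side for the within-subject calculation, and nothing in this mismatch calls for a change to the 240.

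This rests on two-sided alpha, on 570 being an SE and 1970 an SD, and on an n of 9 to 11 for the Section 1.E sizes. At n=8 the SE reading of 570 gives p=0.051, just outside the reported threshold. The check covers only the traceability of the pilot input and the arithmetic from it. It does not assess the conversion to HgbA1C or the choice of a within-subject calculation.

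**What to change.** Recompute the treated-arm AUC change from the existing pilot data. State once the n, which subjects are included, the mean change and its SD, labelled as such, and use that figure in Section 1.E, the Sample Size bullet and the Statistical Power paragraph. If the two figures cover different subjects, say so and justify the one chosen for planning. Give the sidedness of the test. Then restate either the 32 or the 80% so that size and power follow from the input. For example, if 1130 with SD 1970 is confirmed, the plan could state 26 for 80% power or about 88% power at 32 (two-sided 0.05, paired t).

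The cost is a re-reading of data already in hand and a few corrected sentences. The recruited total and the design are unaffected.
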